# 10. DEVIATIONS

#### 10.1 **Deviations**

- 10.1.1 All deviations from this protocol will be reported in the study report. If it is necessary for the protocol to be amended, the amendment and/or a new version of the protocol (Substantial Amendment) must be notified to or approved by IRB before implementation. Local requirements must be followed. If a protocol amendment requires a change to a particular investigational site's ICF, then Sponsor and IRB must be notified. Approval of the revised ICF by Sponsor and by the IRB is required before the revised form is used. Sponsor will distribute amendments and new versions of the protocol to each Investigator and IRB. In general, a non-substantial amendment does not require a notification to or approval by IRB.
- 10.1.2 The Investigator is not allowed to deviate from the protocol except in case of emergency to protect a subject's rights, safety, and wellbeing. In such a case, the Investigator may proceed without prior approval from Sponsor or the IRB. However, the deviation should be documented and reported to Sponsor and the IRB as soon as possible.
- 10.1.3 Any protocol deviation that occurs, which is not approved by the Sponsor, will render the study subject ineligible for continued participation in this clinical study.
- 10.1.4 The Investigator should promptly report any protocol deviations to the Sponsor. It is the responsibility of the Sponsor to report all protocol deviations affecting study subject safety to the IRB in a timely manner.

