#### 4.3 Study Duration

- 4.3.1 The study, as a whole is expected to run for up to 18 months, inclusive of the enrollment period.
- 4.3.2 The minimum planned orthodontic treatment period per subject will be 2 months.
- 4.3.3 The maximum planned orthodontic treatment period per subject will be 8 months, unless a refinement is required.
- 4.3.4 Study subjects will remain on-study until treatment with the final investigational or control device is complete or if the subject wishes to no longer participate in the study (withdraws consent) or Severe non-compliance to protocol as judged by the Investigator and/or Sponsor causing the subject to be withdrawn from the study.

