# 8.9 Treatment Final

- 8.9.1 The following will be collected at final treatment visit (TF).
  - Intraoral scan
  - X-ray (CBCT, CEPH, PAN, and/or FMX)
  - Intraoral and extraoral photographs
  - Final visit worksheet (TF)
  - Post-treatment subject questionnaire
- 8.9.2 Each subject will receive removable retainers following completion of aligner therapy.
- 8.9.3 Participation in this study ends for each subject when:
  - Subjects complete treatment with the investigational or control device and the Investigator determine that a retainer can be ordered.

- When a subject withdraws their consent to continue participating in the study.
- If an Investigator removes a subject from the study due to ineligibility or non-compliance with study protocols.

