#### 8.10 Subject Discontinuation

- 8.10.1 The Investigator and/or the Sponsor may discontinuing a subject if severe non-compliance to the protocol. Subject may also be discontinued due to safety reasons as judged by the Investigator and/or Sponsor.
- 8.10.2 If a subject for any reason desires to no longer participate in the study or continue treatment, they are free to discontinue participation in the study, at any time and without providing a reason for the withdrawal. Discontinuation from the clinical study will not affect future treatment /care of the subject.
- 8.10.3 Subjects who discontinue should always be inquired about the reason(s) for their discontinuation and any potential safety issues. If possible, they should be seen and assessed by an Investigator. The termination section in the eCRF should be completed. Safety events should be followed up. Any study specific material provided to the subject should be collected.

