#### 16.4 Subject Withdrawal

- 16.4.1 During the informed consent process, eligible study subjects will be advised that they are free to withdraw their consent to participate in the study at any time, without prejudice by the Sponsor.
- 16.4.2 Every reasonable effort should be made to ensure that each subject complies with the protocol and completes all study visits. However, a subject may withdraw or be withdrawn from participation if:
  - The subject withdraws consent,
  - CoCR or study Investigators recommend discontinuation in the interest of the subject's safety (i.e., AE-related) or because of significant and irremediable protocol non-compliance,
  - There is a report of a SAE that warrants discontinuation,
  - The subject is lost to follow-up, or
  - The Sponsor or the Institutional Review Board (IRB) terminates the clinical trial.
- 16.4.3 Data for subjects that are withdrawn from the study, but have already completed a portion of the trial, will be retained and used in the statistical analyses described in this protocol.
- 16.4.4 Withdrawals from the study shall be documented, with the primary reason for withdrawal recorded by the Investigator.

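### Section 10.1.3 ends participation for any deviation the sponsor does not approve, which conflicts with 4.3.4 and widens an unblinded sponsor's influence over who reaches the final scan

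*Combined protocol and SAP*

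**What the plan says.** Section 10.1.3: "Any protocol deviation that occurs, which is not approved by the Sponsor, will render the study subject ineligible for continued participation". It does not grade deviations, give criteria for approval, or say whether approval after the event is enough.

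The neighbouring rules are:

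- 10.1.1: "All deviations from this protocol will be reported in the study report".
- 10.1.2: in an emergency, "the Investigator may proceed without prior approval from Sponsor or the IRB". The deviation must then be documented and reported.
- 4.3.4: subjects stay in the study until treatment is complete, consent is withdrawn, or there is "Severe non-compliance to protocol as judged by the Investigator and/or Sponsor" that leads to withdrawal.
- 8.9.3: participation ends "If an Investigator removes a subject from the study due to ineligibility or non-compliance with study protocols". There is no severity word here either.
- 8.10.1: the investigator and/or sponsor "may discontinuing a subject if severe non-compliance to the protocol", or may act for safety.
- 8.10.3: of subjects who discontinue, "If possible, they should be seen and assessed by an Investigator". No intraoral scan is named.
- 16.4.2: a subject may be withdrawn on the recommendation of the sponsor's clinical research centre or the investigators, for safety or "because of significant and irremediable protocol non-compliance".
- 16.4.3 and 16.4.4: data already collected are kept and used, and the main reason for withdrawal is recorded.

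Under 12.2.1 neither sponsor nor investigators are blinded, and the data may be analysed during the trial. Under 9.3.1 and 12.2.4, AIM and accuracy need the scan taken at the end of treatment (TF).

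**The concern.** Sites have two rules that disagree. A visit outside the 4-6 week interval (8.3.4) is a deviation. Under 10.1.3 the subject must leave unless the sponsor approves it; under 4.3.4 the subject stays. Up to 15 sites could apply this differently. A subject removed for non-compliance also loses the second rebate (5.4).

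The statistical stake is the TF scan. A subject removed early has no end-of-treatment scan, and retaining earlier data under 16.4.3 cannot supply one. Whether the subject continues depends on approval by a party that can see the data and that receives progress photographs and tracking worksheets at each visit (8.8.1). Section 7.1.2 names wear compliance as the leading cause of poor tracking, so a link between non-compliance and outcome is plausible on the protocol's own account. The synopsis treats a non-significant difference between arms as evidence of efficacy. Losing poorly tracking Nighttime subjects would therefore favour the claim, and losing poorly tracking control subjects would work against it.

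**Working it through.** **1. The removal rules side by side**

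| Section | Trigger | Decided by | Force |
|---|---|---|---|
| 10.1.3 | any unapproved deviation | sponsor, through approval | mandatory |
| 4.3.4 | severe non-compliance | investigator and/or sponsor | otherwise the subject stays |
| 8.9.3 | ineligibility or non-compliance, no threshold | investigator | participation ends if the investigator removes the subject |
| 8.10.1 | severe non-compliance, or safety | investigator and/or sponsor | permissive |
| 16.4.2 | significant and irremediable non-compliance, or safety | research centre or investigators | permissive |

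Sections 8.10.1 and 16.4.2 are permissive and 8.9.3 has no threshold, so a site can follow 10.1.3 without breaching them. The direct conflict is with 4.3.4. Section 10.1.2 waives only prior approval, so an emergency deviation that the sponsor does not approve later still falls under 10.1.3.

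**2. Which measures lose a value** (9.3.1, brackets and minus sign read as intended)

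- PIM = (TS − TP)/TS × 100. TF is not used, so PIM is unaffected.
- AIM = (TS − TF)/TS × 100. TF is needed.
- Accuracy = 100 − |PIM − AIM|/|AIM| × 100. TF is needed through AIM.

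**3. The plan's own sample size** (12.1.2: SD 1, difference 1, two-sided 5%, power 90%)

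Normal approximation: 2 × (1.960 + 1.282)² = 21.0, so 22 per arm. The two-sample t-test gives 22.02, rounded up to 23, with power 0.912 at 23. The stated 23 is reproduced and is not in dispute.

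**4. Literal application of 10.1.3**

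Assume each visit independently carries a chance p of an unapproved deviation. The documents give no value for p. Subjects left from 50 after v visits = 50(1 − p)^v.

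| p | v = 6 | v = 8 |
|---|---|---|
| 2% | 44.3 | 42.5 |
| 5% | 36.8 | 33.2 |
| 10% | 26.6 | 21.5 |

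Only the last cell falls below the 23 required in 4.2.

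**5. Outcome-linked removal in general**

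Simulation: normal outcomes with SD 1, 50 per arm, two-sided Wilcoxon rank sum test at 5%, 20,000 runs per cell. In the stated arm, the fraction with the lowest z = ρ × outcome + √(1 − ρ²) × noise is removed; in the other arm the same fraction is removed at random. Removal rates and ρ are assumptions. The table gives the probability of a non-significant result when Nighttime is truly worse by the plan's difference of 1 SD.

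| Removal | 10% | 20% | 30% |
|---|---|---|---|
| random in both arms | 0.4% | 1.0% | 1.9% |
| Nighttime only, ρ = 0.25 | 0.7% | 2.4% | 5.7% |
| Nighttime only, ρ = 0.5 | 1.3% | 4.5% | 12.1% |
| both arms, ρ = 0.5 | 0.4% | 0.6% | 1.3% |
| control only, ρ = 0.5 | 0.1% | 0.1% | 0.1% |

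With no removal the figure is 0.2%. If the arms are truly equal, ρ = 0.5 in one arm raises the chance of a significant result from 5% to about 7/12/18%.

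**6. Whether scans at discontinuation could fill the gap**

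TP is the full-course target. A subject stopped at half of plan has accuracy 100 − (0.5/0.5) × 100 = 0%; at a quarter, 100 − (0.75/0.25) × 100 = −200%; at a tenth, 100 − (0.9/0.1) × 100 = −800%. Now assume completers reach 85% of plan on average, stopping points are uniform from 10% to 90% of the course, the between-subject SD is 10 points, the true difference is 0.8 SD, there are 50 per arm, and 10/20/30% stop at random. Pooling the early scans into AIM then gives a non-significant result with probability 8/19/42%, against 5/7/11% for completers only. Accuracy behaves similarly (9/22/45% against 6/8/12%). At an SD of 30 points the cost is no longer material.

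**The case against.** The case against has four strands.

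- **Attribution.** Sections 4.3.4 and 8.10.1 already let the sponsor judge severe non-compliance, a term the protocol does not define, and 8.9.3 lets an investigator remove a subject with no threshold. The figures in step 5 would be the same under those rules alone. This stands: no calculation here isolates what 10.1.3 adds.
- **Approval after the event.** Section 10.1.3 does not ask for prior approval, 10.1.2 mentions prior approval separately, and 10.1.4 has deviations reported promptly to the sponsor. A late visit could therefore be approved afterwards. This is a possible reading and it softens the conflict, but without criteria or timing the outcome still rests on the sponsor's choice.
- **Stacked assumptions.** The larger figures need heavy removal, a strong link with outcome, and confinement to one arm. The documents support none of these, and at 10% removal the excess over random loss is under one percentage point.
- **Existing controls.** Deviations and withdrawal reasons are reported (10.1.1, 16.4.4), an external evaluator scores PAR (12.2.7), and an independent contractor analyses the data (12.2.11). These make removals visible and protect scoring and analysis, but they do not restore a missing scan.

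A reader might infer that the sponsor could use 10.1.3 to shape the result, or that the rule biases the trial towards Nighttime. The documents support neither. They give no deviation rate and no sign of selective approval. AIM does not exist when a deviation is judged, so any link would run imperfectly through photographs and worksheets, and the bias could go either way.

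**Conclusion.** The inconsistency is real and rests on the text alone. Section 10.1.3 is mandatory and has no threshold, it conflicts with 4.3.4, it exceeds 8.10.1 and 16.4.2, and read literally it reaches emergency deviations. It widens an influence the unblinded sponsor already has over who supplies AIM and accuracy.

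The size and direction of any bias are unknown. The simulated figures rest on assumed removal rates and correlations and should not be read as the effect of 10.1.3. Nor is the whole primary comparison at risk: PIM, the measure listed first in 9.3, needs no TF scan, and safety events up to removal are kept and followed. This is a point to consider, mainly an alignment of wording, and not a flaw that undermines the trial.

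**What to change.** Replace 10.1.3 with: *A deviation is documented and reported and does not by itself end participation; a subject is removed only for severe non-compliance as in 8.10.1 or for safety.*

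- Align 4.3.4, 8.9.3 and 16.4.2 with that rule. Leave consent withdrawal, loss to follow-up, trial termination and the treatment-plan eligibility check in 8.1.7 as they are.
- State that emergency deviations under 10.1.2 never end participation, and that sponsor approval of a deviation does not decide who is analysed.
- Analyse every subject with an end-of-treatment TF scan whatever their deviation status, and report missing TF scans by arm and reason.
- If a scan is taken at discontinuation, report it descriptively or as a supportive AIM analysis only. Do not pool it into the main AIM or accuracy comparison: as step 6 shows, early scans can add spread that makes a non-significant result easier to reach.

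The cost is protocol wording. The analysed set will include some less compliant subjects, so the result may look slightly less favourable.

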# 11. ADVERSE EVENTS AND SERIOUS ADVERSE EVENTS

#### 11.1 Adverse Event (AEs)

- 11.1.1 All adverse events must be reported to the divisional complaint officer and regulatory compliance.
- 11.1.2 All Adverse Events (AEs) will be documented and recorded by the Investigator in the eCRF throughout the study period.
  - AE is defined as: Any untoward medical occurrence, unintended disease, effect or injury, or untoward clinical sign in a subject, whether related to the investigational product or not.
  - For example, a rash, bleeding, or blistering appearing on the soft tissue in contact with the investigational device.
  - Another example is clinically significant root resorption.
- 11.1.3 All adverse events shall be reported for that particular study subject's

appointment.

- This documentation should list the event, the cause of the event if known, consequences and resulting actions by the Investigator, or designee, and any other medically pertinent information.
- Where possible, a diagnosis rather than a list of symptoms should be given.
- The intensity to be recorded is the worst intensity experienced during the course of the event. The Investigator should complete all related information, including date(s) of onset, severity, corrective therapies given, outcome, and professional opinion as to whether the AE had a relationship to the investigational device.
- 11.1.4 The Center of Clinical Research (CoCR) team must make the determination of relationship to the investigational device for each recorded AE in the corresponding **eCRF**. The CoCR should decide whether there is a reasonable possibility that the event may have been caused by the investigational device.
- 11.1.5 If there is any valid reason, even if undetermined or untested, for suspecting a possible cause-and-effect relationship between the investigational device and the occurrence of the AE, then the AE should be considered "possibly" or "probably related".
- 11.1.6 Otherwise, if no valid reason exists for suggesting a relationship, then the AE should be classified as "unrelated". The following guidance may also be helpful:
  - Unrelated: There is no medical evidence to suggest that the AE is related to the investigational device. The AE can be readily explained by the subject's underlying medical condition or concomitant therapy or lacks a plausible temporal relationship to investigational device.
  - Possibly Related: A direct cause and effect relationship between the investigational device and the AE has not been demonstrated, but there is a reasonable possibility that the AE was caused by the investigational device.
  - Probably Related: The AE is likely related to the investigational device. This category applies when the experience most likely seems to be related to the investigational device but there is a modest suspicion that it could be related to other causes.
  - Related: There is a direct cause and effect relationship between the AE and the investigational device.
- 11.1.7 The medical assessment of related AE severity will be determined by

using the following definitions:

- Mild: The AE is easily tolerated and does not interfere with usual activity.
- Moderate: The AE interferes with daily activity, but the subject is still able to function.
- Severe: The AE is incapacitating, and the subject is unable to work or complete usual activity, i.e. a serious injury has occurred.
- Life Threatening: The SAE places the subject, in the view of the Investigator, at immediate risk of death from the reaction as it occurred, i.e., it does not include a reaction that had it occurred in a more severe form, might have caused death.
- 11.1.8 Outcome may be classified as resolved, ongoing, resolved with sequelae, or death.
  - Unexpected severe or life threatening related events will be followed until resolved (the subject's health has returned to his/her baseline status or all variables have returned to normal), an outcome is reached, stabilization (the Investigator does not expect any further improvement or worsening of the AE), or the event is otherwise explained regardless of whether the subject is still participating in the study.
  - Where appropriate, medical testing and examinations will be performed to document AE resolution.
- 11.1.9 The types of adverse events that are known to occur with orthodontic treatment include mild to moderate gum pain, inflammation, and redness; allergic reaction to plastic(s) or metal(s); and root resorption.

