# 7. RISKS AND BENEFITS OF PARTICIPATION

#### 7.1 **Risks**

- 7.1.1 The Sponsor has not identified any additional risks by participation in this clinical study. However, there are some risks that have an increased probability of occurrence with a reduced wear time aligner regimen including:
  - Reduced wear time causes teeth to shift while aligner is not worn; treatment takes longer than expected → Treatment Delay
  - Only wearing aligners for 10-12 hours per day can lead to greater subject discomfort when aligners are worn → Subject Discomfort
- 7.1.2 Additionally, there are risks associated with orthodontic treatment in general, including:
  - Discomfort: There may be some discomfort due to wearing an aligner for the first time, as the mouth is very sensitive. As the teeth move, often some discomfort is to be expected, however this usually wears off in a couple of days after each aligner tray

change. Aligners may cause irritation to the surrounding cheeks and lips.

- Allergy: Although rare, some people may be allergic to the plastic in aligners. If the subject knows that they have a plastic allergy or sensitivity, they should notify the Investigator prior to starting aligner therapy. Subject with known allergies to plastic materials are not eligible to participate in this clinical study. If an allergy to the aligner occurs, the Sponsor and/or the Investigator may recommend that treatment be paused and continued using alternative methods.
- Cavities: The surface of teeth may become weaker, and may have more cavities. Excellent oral hygiene will help to prevent this from happening during treatment.
- Resorption: The roots of teeth may become shorter or weaker during treatment. The Sponsor and/or the Investigator may recommend that treatment be paused if this process called root resorption occurs.
- Tooth movement not tracking according to the prescribed treatment plan: This can be caused by several factors; the top factor being subject compliance in wearing aligners the required number of hours per day/night. Treatment time may take longer than expected, or final outcomes may be different than what was planned when aligners are not worn as prescribed.
- X-ray: Standard procedures will be used i.e., all attempts to limit X-ray exposure will be made during the clinical study, including proper shielding.

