# 8. STUDY PROCEDURES

## 8.1 Screening

- 8.1.1 Subjects seeking orthodontic treatment will be screened through the Byte+ network of dental providers. Subjects who opt to receive orthodontic aligner treatment using the Byte® system will be screened for eligibility by the Investigator in the dental office. Screening will be based on potential study subject case complexity and eligibility.
- 8.1.2 Subjects will visit one of the Byte+ network dentists for an initial intraoral scan, x-ray (PAN, CBCT, CEPH and/or FMX), intraoral and extraoral photographs. An X-ray taken within a year from study visit may be used for treatment planning if deemed adequate by the Investigator.
- 8.1.3 Subjects will be screened based on the inclusion and exclusion criteria defined above.
- 8.1.4 Subjects will be informed that the investigational device is being studied for its safety and efficacy in achieving prescribed tooth movement per each individual subject's subject treatment plan and is not currently cleared by the FDA.
- 8.1.5 Informed consent (and parental consent for minors under the age of 18) will be obtained from the subject.

**CONFIDENTIAL:** The information in this study protocol is strictly confidential and is available for review to Investigators, study center personnel, the ethics committee, and the health authorities. It will not be disclosed to third parties without written authorization from the Sponsor, except to obtain informed consent from persons receiving the study treatment. Once the protocol is signed, its terms are binding for all parties.

- 8.1.6 All subjects screened will be documented in the Screening Log maintained at each investigational site.
- 8.1.7 Once the treatment plan is created, the Byte+ account manager will ensure that the subject's prescribed tooth movements are within the constraints and criteria outlined within this study's inclusion/exclusion criteria.
  - If the subject requires movements outside of the study's eligibility criteria, they can continue with their orthodontic treatment with Daytime aligners outside of the confines of this clinical study. In these cases, the Investigator will be informed by the digital lab as to why the subject is not eligible for the study; the Investigator in turn shall notify the subject and withdraw them from the study.

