# 8.3 Study Schedule

Visit	Screening visit	Enrollment visit	Treatment start visit (Ts)	Follow-up visits (Tx - e.g. T1, T2 etc.)	Final visit (T F )
Timepoint			Day 0	T s + every 4-6 weeks during a 2-8 months period	Ts + 8 months
Informed Consent	Х				
Subject eligibility	Х	X4			
Demography	Х				
Medical history 	Х				
Concomitant medications	Х		Х	х	Х
Oral examination	Х				
X-ray 	Х				Х
Clinical photography3	Х			Х	Х
Intraoral scan	Х				Х
Intraoral refinement scan				X5	
Treatment plan (.stl- file) 		Х			
Subject questionnaire				Х	Х
Investigator questionnaire					Х
Aligners provided			Х	Х	
Aligner instructions to subject			Х		
AE/DD collection			Х	Х	Х

 Relevant medical conditions.

 Treatment screening X-ray and Treatment final X-ray (e.g. (PAN, CBCT, CEPH, and/or FMX).

 Intraoral and extraoral photographs.

 Treatment plan generated through Byte portal (final eligibility verification).

 Refinement scan only applicable if deemed needed by the investigtor.

- 8.3.1 Once aligners are manufacturered, the first fifteen (15) aligner stages will be provided to the Investigator. Additional aligner stages in sets up to fifteen (15) are provided to the Investigator to continue treatment after completion of the first fifteen (15) sets.
- 8.3.2 The Investigator will provide the subject with aligners at treatment start and at monthly check-ins with the Investigator at clinic visits.
- 8.3.3 Once the aligner trays are received by the subject, they can start their treatment. The date the aligners are received will be recorded as the start date of each subject's participation (TS). The initial visit worksheet must be completed at this time.
- 8.3.4 The subject visits will be performed monthly (every 4-6 weeks). The Investigator will review the subject's treatment progress, confirm treatment plan and follow-up on any safety events. A visit worksheet must be completed at each visit (T1, T2, T3, etc.).

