**CONFIDENTIAL:** The information in this study protocol is strictly confidential and is available for review to Investigators, study center personnel, the ethics committee, and the health authorities. It will not be disclosed to third parties without written authorization from the Sponsor, except to obtain informed consent from persons receiving the study treatment. Once the protocol is signed, its terms are binding for all parties.

- 8.3.5 The study aims to collect the following data at the following time points:
  - Intraoral scans of the subject prior to the start of treatment (Ts) and end of treatment (TF).
  - X-ray (PAN, CBCT, CEPH, and/or FMX) prior to the start of treatment (Ts) and at the end of treatment final visit (TF).
  - Intraoral and extraoral photographs prior to the start of treatment (Ts), at every check-in visit, and end of treatment final visit (TF).
  - Completed visit worksheet at initial aligner visit (TS), scheduled monthly check in visits (4-6 week intervals: T1, T2, T3, T4, etc.), and final aligner visit (TF).
  - Completed subject questionnaire at check in visits (4-6 week intervals: T1, T2, T3, T4, etc.),
  - Subject post-treatment questionnaire at the end of the treatment (TF).
  - Relevant medical conditions and concomitant medication incl. trade name, dosage, route and start.
  - AE/DD documentation
- 8.3.6 At the final aligner treatment visit  $(T_F)$ , the dentist will complete a final visit worksheet and subject will complete the post-treatment questionnaire.
- 8.3.7 Each subject will receive removable retainers following completion of aligner therapy.

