# 8.6 **Pre-Treatment Period**

- 8.6.1 The following will be collected prior to aligner treatment, and are required for the treatment planning phase of aligner therapy:
  - Intraoral scan
  - X-ray (CBCT, CEPH, PAN and/or FMX)
  - Intraoral and extraoral photographs

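### X-rays are taken before and after treatment and root resorption is a named harm, but the protocol does not require the two films to be compared or a root result recorded for each subject

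*Combined protocol and SAP*

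**What the plan says.** Root resorption appears three times as a harm. Section 7.1.2 lists it among the general risks of orthodontic treatment and says the sponsor or investigator "may recommend that treatment be paused if this process called root resorption occurs". Section 11.1.2 gives it as an illustration of an adverse event: "Another example is clinically significant root resorption". No threshold for clinical significance is given. Section 11.1.9 includes it among event types known to occur, ending the list with "allergic reaction to plastic(s) or metal(s); and root resorption".

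Films are scheduled twice. The footnote to the section 8.3 schedule reads "Treatment screening X-ray and Treatment final X-ray". Section 8.3.5 asks for an X-ray before treatment starts "and at the end of treatment final visit". Section 8.9.1 lists "X-ray (CBCT, CEPH, PAN, and/or FMX" among the TF items.

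The only stated use of a film is planning. Section 8.6.1 says the pre-treatment records "are required for the treatment planning phase of aligner therapy", and section 8.1.2 allows an older baseline film: "An X-ray taken within a year from study visit may be used for treatment planning if deemed adequate by the Investigator". No use is stated for the TF film.

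For safety, section 9.1 compares the incidence of related AEs and SAEs between arms. Section 12.3.2 evaluates events documented from first application of the device until the last aligner is removed.

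**The concern.** Root shortening is a harm for which the protocol already obtains before-and-after images, yet the text leaves its detection to passive reporting. If an investigator compares the two films and sees no shortening, no record is required. If nobody compares them, no record is required either. Both subjects add the same zero to the adverse event count.

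The consequence is for how the safety result can be stated. A report supporting substantial equivalence could show no root resorption in an arm and be unable to say how many subjects that rests on. Investigators are not blinded (12.2.1), so attention to roots could also differ by arm without leaving a trace.

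There is a smaller problem of timing. Section 12.3.2 closes the safety window at removal of the final aligner, and the second film is taken at TF. Read literally, a finding first documented from that film could fall outside the window.

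**Working it through.** **The plan's own figures.** The documents give no figure for root resorption or for any adverse event rate, so there is none to reproduce on this point. The stated 23 per arm (12.1.2) is an efficacy calculation. With SD 1, difference 1, two-sided alpha 0.05 and power 0.90, a two-sample t-test needs 22.02, that is 23 per arm, with power 0.912 at 23. It reproduces, and nothing below depends on it.

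**What happens to each type of record.**

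| Step | Intraoral scans | X-rays |
|---|---|---|
| Obtained before and after treatment | Yes (8.3.5) | Yes (8.3.5) |
| Stated use | PAR score (12.2.4 to 12.2.8) | Treatment planning, baseline film only (8.1.2, 8.6.1) |
| Reader named | External evaluator (12.2.7) | None |
| Before-and-after comparison required | Yes, by formula (12.2.8) | No |
| Per-subject result sent to the eCRF | Yes (12.2.8) | None specified |

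The other safety provisions do not fill the gap. Section 9.2 covers self-reported comfort and pain. Section 12.3.3 evaluates adverse events against known harms once they have been reported. Section 12.2.2 would tabulate a categorical root item if one existed, but the text does not create one.

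**What a zero count would support.** Let k be the number of film pairs in an arm actually compared and assessable. After zero cases in k pairs, the exact (Clopper-Pearson) two-sided 95% upper limit on the rate is

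1 − 0.025^(1/k)

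Section 4.2 gives 50 enrolled per arm and a minimum of 23 evaluable completers per arm. The two smaller values of k are assumptions, chosen only to show how the limit moves.

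| k | Source of k | Calculation | Upper limit |
|---|---|---|---|
| 50 | Enrolment per arm | 1 − 0.025^(1/50) | 7.1% |
| 25 | Assumed: half of 50 | 1 − 0.025^(1/25) | 13.7% |
| 23 | Minimum completers per arm | 1 − 0.025^(1/23) | 14.8% |
| 12 | Assumed: about half of 23 | 1 − 0.025^(1/12) | 26.5% |
| 0 | No pair compared | none | No limit |

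These limits assume that a significant case in a compared pair is always recorded and that compared pairs represent the arm. No resorption rate is assumed. The same zero supports different statements depending on k, and the protocol text does not specify that k be recorded.

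**The safety window.** Section 8.3 schedules adverse event collection at TF, the visit at which the film is taken, and 11.1.3 records the onset date. A case seen on that film can therefore be entered. Section 12.3.2, however, refers to events documented up to aligner removal, and it does not say whether one documented afterwards from the TF film is included.

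**The case against.** The strongest objection is that the forms are not visible. A final visit worksheet is required at TF and study data go into the eCRF; either may already contain a root item. That stands. The point concerns the protocol text, and the remedy is conditional on the forms.

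A reader might infer that a low or zero count would mean nothing, or that the study fails to collect the information. The documents do not support either. Reported cases remain a valid lower bound on what investigators noticed. Section 15.1.2 mentions X-rays among files uploaded to the EDC system, so a later paired reading may be possible, although none is planned.

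A reader might also infer that 12.3.2 excludes findings on the TF film. That is too strong: adverse events are collected at TF, and shortening seen then arose during treatment. What remains is an ambiguity that one sentence settles.

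Nor does the point rest on an untested claim that the nighttime device causes less resorption. Sections 6.1.2 and 6.1.3 attach the reduced-resorption wording to both devices, and the protocol states no resorption hypothesis.

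It is fair to add that other passively reported harms, such as cavities, have the same weakness, and that choosing investigator-reported events as the safety endpoint is legitimate. Resorption differs in that the paired films are already scheduled, so the better record costs almost nothing.

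Finally, the table shows how the limit depends on k; it does not estimate how many films would go unread, which is unknown. Even 23 assessable pairs leave a limit near 15%, so the gain is in being able to state what the count rests on, and it is modest.

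**Conclusion.** The point holds as a minor one. The protocol schedules films before and after treatment and names root resorption as a harm, but it does not require the films to be compared or a per-subject root result to be recorded. A zero count cannot be read as an incidence, because the number of subjects examined is not specified. If all pairs were assessable and none showed a significant case, the upper limit would be 14.8% at 23 per arm and 7.1% at 50 per arm; with fewer assessable pairs it is higher. The 23 is a minimum number of completers and the 50 allows for no dropout, so both are illustrations. The conclusion rests on the visible text and would fall away if the worksheet or eCRF already records a paired root assessment.

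**What to change.** First check the final visit worksheet and eCRF. If there is no such item:

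- Add one required item, completed by the investigator: root shortening versus baseline film, coded as none / present, not clinically significant / present, clinically significant / not assessable or no TF film.
- Define clinically significant in one line as shortening that needs follow-up, treatment or a change in care. This can be applied at TF, when pausing treatment is no longer a useful criterion.
- State in 12.3.2 that a finding first seen on the TF film counts in the safety evaluation.
- Tabulate the item by arm, with exact 95% confidence intervals among assessable pairs and the number that could not be assessed. Label the table descriptive and leave adverse event reporting as it is.

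The cost is one form item, a one-line definition, one sentence and one table, with no extra film, visit or reader. There are drawbacks. The rating is unblinded. The modality is open and need not match between visits, and the baseline film may be up to a year old, so some pairs will not be assessable. Subjects who stop before TF have no scheduled second film.
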